All mild to moderate AD subjects will be included in the efficacy evaluations of the Mild to Moderate AD cohort. The analysis of the Mild to Moderate AD cohort is based on the group sequential design. Interim analyses in the Mild to Moderate AD cohort will only be performed after the MCI/Prodromal cohort crosses the early success boundary. The early efficacy signal based on the change from baseline of ADCOMS at 18 months is defined as crossing the interim-analysis boundaries for overwhelming efficacy in the mild to moderate AD population. The O'Brien-Fleming (OF) boundaries based on Lan-DeMets alpha spending function will be used to assess overwhelming efficacy. The corresponding OF boundaries based on *P* values will be 0.076, 0.0221, and 0.0423 for the first, second, and final analyses, respectively, according to 2 planned interim analyses at the 60% and 80% information fraction. (revised per Amendment 01)

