The null and alternative hypotheses and the statistical test are the same as those for vMRI. To estimate the sample size for the amyloid PET imaging subgroup at 18 months, a common SD of the change from baseline was estimated at 0.33 and a reasonable mean difference between treatment and placebo was estimated as 0.25 (standardized uptake value ratio [SUVR]). Assuming a moderate dose-response, the best dose would achieve a difference of 0.25 (SUVR) and the middle and low doses would achieve a difference of 0.2 and 0.15 (SUVR), respectively; this would require a total of 100 subjects from all 4 arms at 18 months to achieve 80% power.

9.7.2.2 Sample Size Rationale for the Mild to Moderate AD Cohort (revised per Amendment 01)

ADCOMS at Month 18

The null hypothesis is that there is no difference between active dose and placebo. There are 2 null hypotheses corresponding to 2 active doses. The alternative hypothesis is that at least 1 null hypothesis is false. The null hypotheses will be tested using Dunnett's test with 2-sided alpha of 0.05 as described for the Mild to Moderate AD cohort in [Section 9.7.1.6.2](#). The statistical power was estimated through simulation for the dose-response assumption that the percent reduction in change from baseline of ADCOMS at 18 months compared with placebo would be 33% and 50% corresponding to the 2 doses, respectively. The estimated power for the actual planned 200 mild to moderate AD subjects is approximately 80% assuming a 2-sided alpha of 0.05. (revised per Amendment 01)

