The DSMB will continue to monitor the safety aspects of the study throughout Stage A and Stage B. Details will be provided in the DSMB Charter. The study may be stopped for safety at any time.

The first Bayesian adaptive interim analysis will be conducted when 100 MCI/Prodromal subjects have been randomized into the study (ie, including MCI/Prodromal subjects from Stage A and Stage B). (revised per Amendment 01) Further interim efficacy analyses will be conducted after each additional 50 MCI/Prodromal subjects have been randomized, to a maximum of 500 MCI/Prodromal subjects (ie, at 100, 150, 200, 250, 300, 350, 400, 450, 500 subjects randomized). If the study reaches full randomization, additional interim analyses will be conducted every 3 months until all subjects complete 18 months of treatment. The study will be monitored for futility at each interim analysis. Starting at the interim analysis for 200 subjects, the study will be monitored for success at each interim analysis. Each interim analysis will be conducted on data for the derived ADCOMS.

In addition, at each interim efficacy analysis, response adaptive randomization will be used to update the allocation of new subjects between placebo and active doses according to a predefined automated algorithm.

The Mild to Moderate AD Cohort (revised per Amendment 01)

A group sequential design will be used for the Mild to Moderate AD cohort. (revised per Amendment 01) This design includes 3 looks, 2 interim looks (when 60% and 80% information fractions are achieved) and 1 final look. The information fraction is the number of assessments in all treatment arms divided by the total number of expected assessments. Interim analyses will be performed after the MCI/Prodromal cohort crosses the early success boundary. The corresponding efficacy boundaries will be 0.076, 0.022, and 0.0423 for the first, second, and final analyses, respectively. If the actual information fraction during the interim analyses is different from 60% or 80% at the interim, the efficacy boundaries will be adjusted based on the actual information fraction.

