If early success in the MCI/Prodromal cohort is not achieved before the final analysis that is performed when all subjects have completed 18 months treatment, then only a final analysis will be performed in mild to moderate AD subjects. In the event of futility in the MCI/Prodromal cohort, an analysis will be performed for the Mild to Moderate AD cohort based on the data for mild to moderate AD subjects available at that time. (revised per Amendment 01)

Randomization into the Mild to Moderate AD cohort will remain at a fixed schedule throughout Stage B. (revised per Amendment 01)

The interim analyses in the Mild to Moderate AD cohort will be conducted by an independent analysis group. (revised per Amendment 01)

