The Mild AD cohort: The analysis of the Mild AD cohort is based on the group sequential design. Interim analyses in the Mild AD cohort will only be performed after the MCI/Prodromal cohort crosses the early success boundary. The early efficacy signal based on the change from baseline of ADCOMS at 18 months is defined as crossing the interim-analysis boundaries for overwhelming efficacy in the mild AD population. The O'Brien-Fleming (OF) boundaries based on Lan-DeMets alpha spending function will be used to assess overwhelming efficacy. The corresponding OF boundaries based on *P* values will be 0.076, 0.0221, and 0.0423 for the first, second, and final analyses, respectively, according to 2 planned interim analyses at the 60% and 80% information fraction.

Analysis for the primary endpoint

Primary analysis of primary endpoint

The primary analysis will be based on MCI/Prodromal subjects from the FAS with the prespecified censoring rule applied. The primary endpoint is the change from baseline to 18 months in the derived ADCOMS. The dose-response of the primary endpoint is modelled with a first-order normal dynamic linear model, where Normal and Inverse-Gamma priors are used. The primary efficacy analysis will calculate the Bayesian posterior probability that the dose identified is the most likely ED₉₀ dose that achieves 25% improvement over the placebo arm. At each interim analysis and the final analysis, 2 Bayesian probabilities will be summarized for each active dose: the probability it is the ED₉₀ dose and the probability of achieving 25% improvement over the placebo arm.

For the clinical efficacy data (ie, derived ADCOMS, MMSE, ADAS-cog, etc), subjects will be censored at the time of initiation of treatment with AChEIs or memantine, if they were not on these medications at the time of Baseline cognitive assessment (Visit 2), and will be censored at the time of dose adjustment of AChEIs or memantine if they were already on stable treatment with these medications at the time of Baseline cognitive assessment

(Visit 2). The value of the primary endpoint for censored subjects will be imputed using data up to the censoring time and Bayesian longitudinal modeling.

Sensitivity analyses of primary endpoint

After unblinding, the primary endpoint will be analyzed using the Bayesian methods described above as well as conventional statistical methods. The following additional Bayesian analyses will be conducted as sensitivity analyses:

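### Section 9.7.3 gives 0.0423 as the final Mild to Moderate AD level without exempting the path on which no interim look is held, so that path, read literally, leaves 0.0077 of alpha unused and has about 78% power

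*Protocol*

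**What the plan says.** Section 9.7.3 sets out the design for this cohort: "This design includes 3 looks, 2 interim looks (when 60% and 80% information fractions are achieved) and 1 final look". It then lists the levels: "The corresponding efficacy boundaries will be 0.076, 0.022, and 0.0423 for the first, second, and final analyses, respectively". The Synopsis (Efficacy Analyses) and Section 9.7.1.6 repeat the list: "The corresponding OF boundaries based on *P* values will be 0.076, 0.0221, and 0.0423 for the first, second, and final analyses, respectively". Section 9.7.1.6 names the method: "boundaries based on Lan-DeMets alpha spending function will be used to assess overwhelming efficacy".

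Interim looks in this cohort depend on the other cohort. They are held only after the MCI/Prodromal cohort crosses its early success boundary. If it has not done so before the final analysis, "then only a final analysis will be performed in mild to moderate AD subjects". If the MCI/Prodromal cohort meets futility, one analysis of the AD subjects is made on the data available at that time. Section 9.7.3 gives no significance level for either of these two branches. Its adjustment clause recomputes the boundaries when an interim look falls at an information fraction other than 60% or 80%. It does not mention looks that are never held.

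Section 9.7.2.2 plans the same comparison at the overall level: "The null hypotheses will be tested using Dunnett's test with 2-sided alpha of 0.05". It adds: "The estimated power for the actual planned 200 mild to moderate AD subjects is approximately 80% assuming a 2-sided alpha of 0.05". Section 9.7 sets 5% two-sided for all tests except the Bayesian methods on the primary endpoint.

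**The concern.** A nominal 0.0423 at a third look is the price of two earlier opportunities to reject. On the final-only branch there were none, so that price has no purpose. Section 9.7.3 nevertheless uses the same term, final analysis, for the third look of three and for the only look. The one level it attaches to that term is 0.0423.

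A Dunnett-adjusted p value between 0.0423 and 0.05 on this branch would be judged a failure by a literal reader of Section 9.7.3 and a success by a reader of Sections 9.7 and 9.7.2.2. The branch is an ordinary one. It applies whenever the MCI/Prodromal cohort meets neither early success nor futility before all subjects complete 18 months.

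**Working it through.** **Inputs.** Looks at 60%, 80% and 100% information, Lan-DeMets O'Brien-Fleming spending, listed final level 0.0423 (Sections 9.7.1.6 and 9.7.3). Two-sided alpha 0.05, Dunnett, two doses against placebo, reductions of 33% and 50%, 200 subjects, approximately 80% power (Section 9.7.2.2). Stage B allocation 1:1:1 (Section 9.7.4). The protocol gives no placebo change, SD or attrition for this cohort, so the 80% is taken as the starting point and cannot be checked.

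**1. Reproduce the listed level.** Cumulative two-sided spending is α(t) = 4[1 − Φ(2.2414/√t)], where 2.2414 is the normal quantile for an upper tail of 0.0125.

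| Look | Cumulative alpha | Boundary z | Nominal two-sided P |
|---|---|---|---|
| 60% | 0.0076 | 2.669 | 0.0076 |
| 80% | 0.0244 | 2.289 | 0.0221 |
| 100% | 0.0500 | 2.031 | 0.0423 |

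So 0.0423 is the third-look level of an overall 0.05 design. The second value also agrees. The first is printed as 0.076 where the design gives 0.0076; that is a separate matter.

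**2. Remove the interim looks.** With one analysis at full information the same function releases α(1) = 0.0500. Keeping 0.0423 leaves 0.0500 − 0.0423 = 0.0077 unspent. The reverse error also matters: simulation of 0.0076, 0.0221 and then 0.05 after both looks gives an overall error of 0.0564. So 0.0423 must stay for the three-look path.

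**3. Power, single comparison.** The drift for 80% power at 0.05 is 1.960 + 0.842 = 2.802. At 0.0423 the critical value is 2.031, and power is Φ(2.802 − 2.031) = Φ(0.771) = 0.780.

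**4. Power, Dunnett, at least one dose.** With three equal arms the two test statistics have correlation 0.5, and their means are in the ratio 0.33/0.50 = 0.66. The critical values are 2.212 at 0.05 and 2.279 at 0.0423. A mean of 2.933 for the higher dose gives power 0.800 at 0.05. The same mean gives 0.780 at 0.0423.

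**5. Cost in subjects.** [(2.031 + 0.842)/(1.960 + 0.842)]² = 1.051, so about 5% more subjects would restore 80% at 0.0423: roughly 70 per arm instead of 200/3 = 66.7.

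**6. Other reading of the 80%.** If it is the overall power of the three-look design, the drift is 2.836. Final-only power is then 79.0% at 0.0423 and 80.9% at 0.05.

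**7. Only one look held.** The final level becomes 0.0476 after a look at 60% only, and 0.0429 after a look at 80% only.

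**8. Futility branch.** The information available is unknown. Dunnett power under the assumptions of step 4:

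| Assumed information fraction | At 0.0423 | At 0.05 |
|---|---|---|
| 0.5 | 47% | 50% |
| 0.6 | 55% | 58% |
| 0.8 | 68% | 70% |
| 0.9 | 73% | 76% |

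**The case against.** A reader might infer that the protocol assigns this test two conflicting alphas. It does not. 0.0423 is a nominal boundary and 0.05 is the overall level of the same design, and step 1 derives one from the other. Quoting the overall level in a sample size section and the nominal levels in an interim section is normal practice.

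It can also be said that the text already points to 0.05. The Synopsis and Section 9.7.1.6 link the listed values to two planned looks at 60% and 80%. Section 9.7 supplies a 5% default. The named spending function releases the full 0.05 when nothing was spent earlier. No sentence expressly orders 0.0423 where no look was held, and an analysis plan that is not shown may settle the matter. All of this stands, and it makes the loss conditional on the literal reading.

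It does not remove the gap. The protocol itself fixes the number and creates the branch, and the only adjustment clause it gives covers looks held at other fractions.

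A further tempting reading is that 78% power applies to every path without an interim look. It does not apply at MCI/Prodromal futility, where the data are incomplete and power depends on how much is available.

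**Conclusion.** The point holds as a minor one. Section 9.7.3 and the Synopsis give 0.0423 for the final AD analysis without exempting the final-only path, where no alpha has been spent. Applied there, the type I error is 4.23% instead of 5%, and power falls by about 2 points, from approximately 80% to about 78% (79.0% against 80.9% if the 80% is three-look power).

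These figures assume 200 subjects in three equal arms and take the stated power as given. Section 9.3 counts Stage A subjects within the 200, and Section 9.7.4 randomizes Stage A subjects to a 5 mg arm as well. The three compared arms may therefore hold fewer than 200, and actual power could differ from the stated 80% for that reason too. There is no inflation of error on this path. The defect is unused alpha and an undefined verdict for adjusted p values between 0.0423 and 0.05.

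**What to change.** Add to Section 9.7.3, and match in the Synopsis: if no interim efficacy look was taken in the Mild to Moderate AD cohort, its final analysis is tested at two-sided 0.05 with Dunnett; the level 0.0423 applies only when both planned looks were taken, and is otherwise recomputed from the Lan-DeMets function for the looks actually held.

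For the analysis at MCI/Prodromal futility, state its status. If the full 0.05 is to be used there, say that it is the only efficacy analysis of this cohort. If a later analysis could follow, the spending function allows only the amount for the information reached, for example 0.0076 at 60%.

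The cost is two or three sentences, with no change to sample size or conduct. Type I error stays at 5% because no alpha was spent earlier on these paths. The change should be made before any unblinded AD efficacy result is seen.

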9.7.4 Other Statistical/Analytical Issues

Adaptive Randomization in the MCI/Prodromal Cohort

Randomization to placebo or 1 of 3 dose groups of E2609 will be fixed for the first 100 MCI/Prodromal subjects randomized in the study (1:1:1:1; placebo to each of the 3 active doses for the first 100 MCI/Prodromal subjects randomized, including those randomized from both Stage A and Stage B). Thereafter, randomization probabilities to each treatment group will be updated at each interim analysis, such that the randomization probability will be increased for the placebo group and dosage groups that represent the potential target dose (ED_{90}), and simultaneously decreased for other active arms. (revised per Amendment 01)

Randomization in the Mild to Moderate AD Cohort (revised per Amendment 01)

In Stage A, the mild to moderate AD subjects will be randomized to placebo or 1 of 3 E2609 dose groups (5 mg, 15 mg, and 50 mg of E2609) at a 1:1:1:1 ratio, while in Stage B, the mild to moderate AD subjects will be randomized to placebo or 1 of 2 E2609 dose groups (15 mg and 50 mg E2609) at a 1:1:1 ratio. (revised per Amendment 01)

Stratification (revised per Amendment 01)

Within the 2 clinical cohorts (MCI/Prodromal and mild to moderate AD), subjects will be stratified at randomization by *ApoE4* status (positive or negative) and prior treatment with AChEIs or memantine or both (yes or no). (revised per Amendment 01)

9.7.5 Procedure for Revising the Statistical Analysis Plan

If the statistical analysis plan needs to be revised after the study starts, the sponsor will determine how the revision impacts the study and how the revision should be implemented. The details of the revision will be documented and described in the clinical study report.

11 PROCEDURES AND INSTRUCTIONS (ADMINISTRATIVE PROCEDURES)

11.1 Changes to the Protocol

Any change to the protocol requires a written protocol amendment or administrative change that must be approved by the sponsor before implementation. Amendments specifically affecting the safety of subjects, the scope of the investigation, or the scientific quality of the study require submission to health or regulatory authorities as well as additional approval by the applicable IRBs/IECs. These requirements should in no way prevent any immediate action from being taken by the investigator, or by the sponsor, in the interest of preserving the safety of all subjects included in the study. If the investigator determines that an immediate change to or deviation from the protocol is necessary for safety reasons to eliminate an immediate hazard to the subjects, the sponsor's medical monitor and the IRB/IEC for the site must be notified immediately. The sponsor must notify the health or regulatory authority as required per local regulations.

Protocol amendments that affect only administrative aspects of the study may not require submission to health or regulatory authority or the IRB/IEC, but the health or regulatory authority and IRB/IEC (or if regionally required the head of the medical institution) should be kept informed of such changes as required by local regulations. In these cases, the sponsor may be required to send a letter to the IRB/IEC and the Competent Authorities (or, if regionally required, the head of the medical institution) detailing such changes.

11.2 Adherence to the Protocol

The investigator will conduct the study in strict accordance with the protocol (refer to ICH E6, Section 4.5).

11.3 Monitoring Procedures

The sponsor's or CRO's CRA will maintain contact with the investigator and designated staff by telephone, letter, or email between study visits. Monitoring visits to each site, and potential remote source document verification, will be conducted by the assigned CRA as described in the monitoring plan. The investigator (or if regionally required, the head of the medical institution) will allow the CRA to inspect the clinical, laboratory, and pharmacy facilities to assure compliance with GCP and local regulatory requirements. The eCRFs and subject's corresponding original medical records (source documents) are to be fully available for review by the sponsor's representatives at regular intervals. These reviews verify adherence to study protocol and data accuracy in accordance with local regulations. All records at the site are subject to inspection by the local auditing agency and to IRB/IEC review.

In accordance with ICH E6, Section 1.52, source documents include, but are not limited to, the following:

- Clinic, office, or hospital charts
- Copies or transcribed health care provider notes that have been certified for accuracy after production
- Recorded data from automated instruments such as IxRS, x-rays, and other imaging reports (eg, sonograms, computed tomography scans, MRIs, radioactive images, ECGs, rhythm strips, electroencephalography, polysomnographs, pulmonary function tests) regardless of how these images are stored, including microfiche and photographic negatives
- Pain, quality of life, or medical history questionnaires completed by subjects
- Records of telephone contacts
- Diaries or evaluation checklists
- Drug distribution and accountability logs maintained in pharmacies or by research personnel
- Laboratory results and other laboratory test outputs (eg, urine pregnancy test result documentation and urine dip-sticks)
- Correspondence regarding a study subject's treatment between physicians or memoranda sent to the IRBs/IECs
- CRF components (eg, questionnaires) that are completed directly by subjects and serve as their own source

11.4 Recording of Data

An eCRF is required and must be completed for each subject by qualified and authorized personnel. All data on the eCRF must reflect the corresponding source document, except when a section of the eCRF itself is used as the source document. Any correction to entries made on the eCRF must be documented in a valid audit trail where the correction is dated, the individual making the correction is identified, the reason for the change is stated, and the original data are not obscured. Only data required by the protocol for the purposes of the study should be collected.

The investigator must sign each eCRF. The investigator will report the eCRFs to the sponsor and retain a copy of the eCRFs.

11.5 Identification of Source Data

All data to be recorded on the eCRF must reflect the corresponding source documents.

11.6 Retention of Records

The circumstances of completion or termination of the study notwithstanding, the investigator (or if regionally required, the head of the medical institution or the designated representative) is responsible for retaining all study documents, including but not limited to the protocol, copies of eCRFs, the Investigator's Brochure, and regulatory agency registration documents (eg, Form FDA 1572, ICFs, and IRB/IEC correspondence). The site should plan to retain study documents, as directed by the sponsor, for at least 2 years after the last approval of a marketing application in an ICH region and until there are no pending or contemplated marketing applications in an ICH region or at least 3 years have elapsed since the formal discontinuation of clinical development of the investigational product.

It is requested that at the completion of the required retention period, or should the investigator retire or relocate, the investigator contact the sponsor, allowing the sponsor the option of permanently retaining the study records.

11.7 Auditing Procedures and Inspection

In addition to routine monitoring procedures, the sponsor's Clinical Quality Assurance department conducts audits of clinical research activities in accordance with the sponsor's standard operating procedures to evaluate compliance with the principles of ICH GCP and all applicable local regulations. If a government regulatory authority requests an inspection during the study or after its completion, the investigator must inform the sponsor immediately.

